Study Protocol Title:

A Prospective Pilot Study to Evaluate Efficacy and Safety of Euflexxa for the Treatment of Osteoarthritis

Principal Investigator: [name] **[contact]

Funding Sponsor:

Ferring Pharmaceuticals, Parsippany, NJ

Project Contact: [name]

Senior Director, Medical Affairs – Orthopaedics

Ferring Pharmaceuticals Inc.

[name]

[contact] [contact]

:

Regulatory Sponsor:

This study is an Investigator Initiated research trial. Each study site will be considered its own regulatory sponsor and is responsible for internal data monitoring and any study reporting required by ClinicalTrials.gov.

Introduction

Knee osteoarthritis is one of the most common joint disorders which affects a large portion of aging population¹. One of the treatment options is viscosupplementation, which is intra-articular injection of hyaluronic acid IA-HA. Multiple studies have been conducted on the safety and efficacy of IA-HA, but none of the studies, to our knowledge, have evaluated the synovial fluid markers. Therefore, it becomes essential to investigate the effect of IA-HA on the concentration of various synovial fluid markers.

Background and Significance

The FLEXX trial² was the first well-controlled, randomized, double-blind, multicenter study evaluating the efficacy of Euflexxa (1% sodium hyaluronate) therapy for knee osteoarthritis. Five-hundred-and-eighty patients were randomized to receive either Euflexxa or normal saline. There were significant improvements in the Visual analogue scale score Osteoarthritis Research Society International responder index, HRQoL, and function at 26-week follow-up². However, the FLEXX trial did not evaluate changes in synovial fluid bio-marker levels.

The hypothesis of this study is that Euflexxa therapy for knee osteoarthritis will improve levels of inflammatory and degenerative synovial fluid bio-markers in patients with knee osteoarthritis. In addition, we also hypothesize that Euflexxa therapy will improve pain, clinical outcomes, and time to total knee arthroplasty.

Study Design

Methods

- A prospective pilot study

Sample

- 25 subjects for a pilot study

Inclusion criteria:

- 1) OA of the knee by American College of Rheumatology criteria
- 2) Those who failed non-pharmacological measures or simple analgesics
- 3) moderate to severe pain score of 41 to 90 mm recorded on 100-mm visual analog scale (VAS) immediately following a 50-foot walk
- 4) bilateral standing anterior-posterior radiograph demonstrating Kellgren and Lawrence grade 2 or 3 OA of the target knee
- 5) ability and willingness to use only acetaminophen as the analgesic (rescue) study medication
- 6) unassisted walking 50 feet on a flat surface and going up and down stairs
- 7) willingness and ability to complete efficacy and safety questionnaires

Exclusion criteria:

1. Age less than 18 years
2. any major injury to the target knee within the prior 12 months
3. any surgery to the target knee within the prior 12 months
4. surgery to the contralateral knee or other weight-bearing
5. inflammatory arthropathies
6. gout or pseudogout within the previous 6 months
7. radiographic acute fracture, severe loss of bone density, avascular necrosis, and/or severe bone or joint deformity in the target knee

8. osteonecrosis of either knee
9. fibromyalgia, pes anserine bursitis, lumbar radiculopathy, and/or neurogenic or vascular claudication
10. target knee joint infection or skin disorder/ infection within the previous 6 months
11. symptomatic OA of the hips, spine, or ankle; known hypersensitivity to acetaminophen, IA-BioHA, or phosphate-buffered saline solution
12. Women of childbearing potential who are pregnant, nursing, or planning to become pregnant, and those who do not agree to remain on an acceptable method of birth control throughout the study
13. history of immune disorders; vascular insufficiency of lower limbs or peripheral neuropathy
14. current treatment or treatment of cancer within the previous 2 years (excluding basal cell or squamous cell carcinoma of the skin)
15. active liver or renal disease
16. any clinically significant abnormal laboratory value [to be defined in detail at a later point]
17. any intercurrent chronic disease or condition that might interfere with the completion of the study
18. participation in any experimental device study within the prior 6 months or any experimental drug study within the prior month

Research Procedures – Define the data to be collected to answer the hypothesis/research question(s)

Injection:

Twenty five patients will be assigned to receive Euflexxa (n=10) (1% sodium hyaluronate). Three consecutive injections (2 sets) will be performed with 1 weeks' time in-between each injection at the index visit (Index visit, Week 1±3 days and Week 2±3 days) and at six months (6 month, Week 7, and Week 8).

Aspiration (primary outcome)

Knee joint aspiration will be performed prior to the initial injection (at visit 1), and at visit 4 (6 weeks \pm 1 week) and visit 6 (6-months \pm 2 weeks) as outlined in previous studies which measured synovial fluid biomarkers.^{3,4} Following aspiration, the synovial fluid will be placed on ice as soon as possible, and transported to the lab. In the lab it will be centrifuged at 1,500 rpm for 10 minutes at a temperature of 4°C. Subsequently, the supernatant fluid will be removed and 1mL of Trizol will be added to the cell pellet (sediment). The pellet will be stored at -20°C and shipped to Rush University Medical Center for future RNA sequencing analyses (cell markers and TLR/Nfk-b Pathway genes). The results of these tests (RNA sequencing) will not be shared with the patients, and will not be documented in the medical record.

The supernatant fluid will be used for biomarker analysis. Remaining fluid will be frozen and stored for future research. The purpose of the aspiration is to measure the following synovial fluid bio-markers^{3,4}:

Biomarker	Measurement Method
1. Chondroitin 6-sulfate (C6S)	FACE ¹ and sizing
2. Chondroitin 4-sulfate (C4S)	FACE and sizing
3. Keratan sulfate (KS)	FACE and sizing
4. Hyaluronate (HA)	FACE and sizing
5. Matrix metalloproteinase-3 (MMP-3)	ELISA ²
6. Tissue inhibitor of MMP-1 (TIMP-1)	ELISA
7. Tissue Necrosis Factor-alpha (TNF- α)	ELISA
8. IL-6	ELISA
9. Tumor necrosis factor-stimulated gene 6 (TSG-6)	ELISA
10. Inter alpha inhibitor (IaI)	Western Blot

¹ FACE- Fluorophore-assisted carbohydrate electrophoresis

² ELISA – Enzyme-linked immunosorbent assay

Secondary outcome measurements⁵

- The effect of Euflexxa on pain, using the Visual Analogue Scale (VAS)
- The effect of Euflexxa on Clinical outcomes using the following standardized scales and questionnaires:
 1. Western Ontario and McMaster Universities Arthritis Index (WOMAC)
 2. Knee Society Score (KSS)
 3. Veterans Rand-12 item form (VR-12)
 4. UCLA activity score (UCLA)
- Time to total knee arthroplasty, which will be collected by asking questions regarding whether or not the patient received a total knee arthroplasty will be asked at each visit (Knee surgery?)(**Table 1**).

Visual analogue scale (VAS), Western Ontario and McMaster Universities Arthritis Index (WOMAC), Knee Society Score (KSS), Short Form-12 (SF-12), UCLA activity score (UCLA), and questions regarding whether or not the patient received a total knee arthroplasty will be asked at each visit (**Table 1**).

	Index visit /Visit 1	Visit 2 (Week 1 ± 3 days)	Visit 3 (Week 2 ± 3 days)	Visit 4 (Week-6±2 weeks) (visit 4)	Visit 5 (3- month±2 weeks)	Visit 6 (6- month±4 weeks)	Visit 7 (One week from visit 6 ± 3 days)	Visit 8 (Two weeks from visit 6 ± 3 days)	Visit 9 (1-year±2 months)	Visit 10 (2- year±2 months)
Aspiration	X			X		X				
Injection	X	X	X			X	X	X		
VAS	X	X	X	X	X	X			X	X
WOMAC	X	X	X	X	X	X			X	X
KSS	X	X	X	X	X	X			X	X
SF-12	X	X	X	X	X	X			X	X
UCLA	X	X	X	X	X	X			X	X
Knee Surgery?	X	X	X	X	X	X			X	X
Adverse Events	X	X	X	X	X	X	X	X	X	X

The subjects will be paid a stipend of 40 dollars for each visit (visit 1 to visit 10). Thus, a total of 400\$ will be paid to the patient if all the visits are completed. Additionally, the subjects will be provided free parking for all the visits.

Research Protocol Guidelines (continued)

Data Analysis

Unless otherwise indicated, all testing of statistical significance will be two-sided, and a difference resulting in a p-value of less than or equal to 0.05 will be considered statistically significant. Also, after each analysis, General Linear Models (GLM) will be used to control for possible confounders, including BMI, gender, age and ethnicity.

Adverse Events and Data Monitoring Committee(DMC)

Procedural safety will be documented in this study through patient and surgeon reported adverse events. AEs will be documented for all cases in this study.

An Unanticipated Problem Involving Risks to Participants or Others is any event that (1) is unforeseen, (2) caused harm or placed a person at increased risk of harm, and (3) is related to the research procedures.

An Adverse Event (AE) is any untoward or unfavorable medical occurrence, including any abnormal sign (for example, abnormal physical exam or laboratory finding), symptoms, or disease. Adverse events can encompass both physical and psychological harms.

An Internal Adverse Event (AE) is an untoward medical occurrence, which occurs to participants in research conducted by Cleveland Clinic and/or Cleveland Clinic is the IRB of record.

External Adverse Event (AE) is an untoward medical occurrence experienced by subjects enrolled at other institutions for the same study approved at Cleveland Clinic or a different study using the same study drug/device.

A Serious Adverse Event (SAE) is any adverse experience that results in any of the following outcomes:

- death
- a life-threatening experience
- inpatient hospitalization or prolongation of existing hospitalization
- a persistent or significant disability/incapacity
- a congenital anomaly/birth defect
- Important medical events that may not result in death, be life-threatening, or require hospitalization may be considered a serious adverse drug experience when, based upon appropriate medical judgment, they may jeopardize the patient or subject and may require medical or surgical intervention to prevent one of the outcomes listed in this definition.

An Unexpected Adverse Event means any AE not previously known or included in the current Investigator's Brochure, consent form or other risk information.

Related/Possibly Related means there must be reasonable evidence to suggest the event was caused by the drug, device or investigational intervention.

1. Internal Serious Adverse Events (events that occur to participants enrolled in research being conducted by Cleveland Clinic or when Cleveland Clinic is the IRB of record) must be promptly reported to the IRB using the IRB AE Report Form within 10 working days from discovery/awareness which meet any of the following criteria as assessed by the PI/Co-I:
 - a) Serious, Unexpected and Related/Possibly Related.

b) AE's determined to be occurring at a significantly higher frequency or severity than expected.

c) Other Unexpected AE's, regardless of severity, that changes the risk benefit ratio of the study and results in changes to the Research Protocol or Informed Consent process/document.

All Internal SAEs are also reported at continuing review using the AE Summary Log.

2. External Serious Adverse Events (events experienced by subjects enrolled at other institutions for the same study approved at Cleveland Clinic or a different study using the same study device/drug) are reportable to the IRB using the IRB AE Report Form within 10 working days from discovery/awareness when:

a. The External SAE report includes reasonable evidence as assessed by a central monitoring entity [Coordinating or Statistical Center, or a Data Safety Monitoring Board (DSMB) or Data Monitoring

Committee (DMC)] that the event is Serious, Unexpected, and Related/Possibly Related AND places the subjects or others at a greater risk of physical or psychological harm than was previously known or recognized. This will require a change in the protocol and/or consent document.

b. External SAE reports provided by the Sponsor to the investigator indicating the event is Serious, Unexpected and Related/Possibly related but without reasonable evidence or DSMB/DMC determination of greater risk are not reportable to the IRB within the

10 day window. Without Sponsor evidence or assessment the implications of the event cannot be determined by the research team and therefore need not be reviewed. These SAE's shall be placed on the AE Summary log to be submitted at the annual continuing renewal.

3. DEATHS are to be reported to the IRB using the IRB AE Report Form according to the following guidelines:

a) Internal Death

- Related/possibly related whether expected or unexpected – within 5 working days from discovery/awareness

- not related and expected – at time of continuing review

- Not related and unexpected – at time of continuing review except cancer studies

- Cancer: Not related and unexpected within 10 working days from discovery/awareness

b) External Death

Related/possibly related and unexpected – within 5 working days from discovery/awareness not related whether expected or unexpected – at time of continuing review related/possibly related and expected – at time of continuing review

c) ALL Deaths are also reported at time of continuing review using the AE summary log.

4. Non-serious Adverse events (Internal and External) that are both Related/Possibly related and unexpected are reported on the AE Summary Log at time of continuing review to assess trends.

5. An IRB staff (a qualified, licensed practitioner assigned to this function by the IRB chair and IRB Executive Director) reviews Adverse Event Reports to determine whether they represent Unanticipated Problem Involving Risks to Participants or

Others. Events that are assessed, by either the IRB Staff or Investigator, to place subjects or others at a greater risk of harm than was previously known or recognized, or changes the risk/benefit ratio of the study, or requires a change in the protocol and/or consent document are referred to Full Board for review under Policy #70.

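### Nothing limits or records a recent marketed intra-articular injection or NSAID use before Visit 1, so carry-over can bias the only pre-treatment sample of the primary biomarker outcome

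*Combined protocol and SAP*

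**What the plan says.** The protocol lists 7 inclusion and 18 exclusion items. Several carry look-back windows: 12 months for injury or surgery to the target knee, 6 months for gout or joint infection, and 2 years for cancer treatment. Exclusion 18 covers "participation in any experimental device study within the prior 6 months or any experimental drug study within the prior month".

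The other items that come near prior treatment are these:

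- Inclusion 2 admits "Those who failed non-pharmacological measures or simple analgesics".
- Inclusion 5 asks for "ability and willingness to use only acetaminophen as the analgesic (rescue) study medication".
- Exclusion 11 mentions the product class only as "known hypersensitivity to acetaminophen, IA-BioHA, or phosphate-buffered saline solution".
- Exclusion 17 covers "any intercurrent chronic disease or condition that might interfere with the completion of the study".

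The section on aspiration, which is labelled the primary outcome, states: "Knee joint aspiration will be performed prior to the initial injection (at visit 1), and at visit 4", and a third sample follows at Visit 6 (6 months). Table 1 opens with the index visit, where both the first aspirate and the first injection fall. Its rows are aspiration, injection, five scales, a knee-surgery question and adverse events. The Data Analysis section sets two-sided testing at 0.05 and a general linear model for possible confounders, of which it names age, gender, ethnicity and BMI.

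**The concern.** Everyone in the study receives Euflexxa, so there is no second arm in which a drift unrelated to the study product would also appear and cancel. The protocol does not define the primary contrast, but with one arm and samples at Visits 1, 4 and 6 the evident one is change from Visit 1. That contrast is only as good as the Visit 1 sample.

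As written, a patient who had a course of marketed hyaluronate or a corticosteroid injection in the same knee a few weeks or months earlier is eligible. If that treatment is still acting on the joint fluid at Visit 1 and wears off later, the wearing-off is counted as change on Euflexxa. The same holds for a patient whose NSAID use ends near Visit 1. No injection or medication history is scheduled, so the analyst could neither see the problem nor adjust for it afterwards.

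**Working it through.** **Text check.** Each place that could close the gap was read for whether it does.

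- Exclusion 18 reaches experimental studies only, so a marketed product given in ordinary care falls outside it.
- Exclusion 11 concerns hypersensitivity, not recent use.
- Exclusion 17 concerns diseases or conditions that threaten completion, not earlier treatment.
- Inclusion 2 sets no limit on injections or NSAIDs.
- Inclusion 5 states a willingness and gives no start time.
- Table 1 has no row for prior or concomitant treatment.
- The list of model covariates is open-ended, but a covariate that is not collected cannot be added to it.

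The gap is therefore present, and no other section supplies the missing rule or record.

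**Direction for hyaluronate.** Hyaluronate is marker 4 of 10 and is also the injected substance. Residual product from an earlier course adds to the Visit 1 value. If it clears by the later sample, follow-up minus baseline is pushed downward: a spurious fall, or a masked rise.

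**Size for a suppressed inflammatory marker.** The plan states no figure that could be reproduced here, and the documents give neither a prevalence nor an effect on any marker. Assumptions:

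- a share f of patients has a Visit 1 value lowered by a proportion s;
- those values fully recover by follow-up;
- Euflexxa has no effect;
- change is summarised as a ratio of geometric means, which the plan does not specify.

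On the log scale the mean baseline is too low by −f·ln(1−s), so

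spurious rise = exp(−f·ln(1−s)) − 1.

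- f = 0.1, s = 0.3: exp(0.1 × 0.357) − 1 = 3.6%
- f = 0.2, s = 0.5: exp(0.2 × 0.693) − 1 = 14.9%
- f = 0.4, s = 0.5: exp(0.4 × 0.693) − 1 = 32.0%

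**Effect on a test.** As a second illustration, take a two-sided paired t-test at 0.05 with n = 25 and no drug effect. A share f of patients has a baseline shifted by d standard deviations (SD) of the change score. The mean bias is f·d and the variance becomes 1 + f(1−f)d². The rejection probability comes from the noncentral t with noncentrality f·d·√25 / √(1 + f(1−f)d²). This is approximate, because a mixture of shifted and unshifted patients is not exactly normal.

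- f = 0.2, d = 0.5: bias 0.10 SD, rejection 7.6%
- f = 0.2, d = 1.0: bias 0.20 SD, rejection 14.5%
- f = 0.4, d = 1.0: bias 0.40 SD, rejection 40.7%

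Over f = 0.1 to 0.4 and d = 0.5 to 1.5, the rejection probability per marker runs from 5.6% to 64.1%, against the nominal 5%. The bias runs from 0.05 to 0.60 SD. For scale, the change detectable with 80% power at n = 25 is 0.58 SD. The Injection section also gives n=10 in the sentence that assigns 25 patients, which must be reconciled separately. At n = 10 the rejection range is 5.2% to 27.7%.

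**The case against.** The strongest reply is that the omission is certain but its consequence is not. Much of that stands.

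- A reader might infer that carry-over does distort the baseline. The documents do not show that any patient had a recent injection or NSAID. They support only that it can.
- A reader might take the Background section's 26-week result as proof of lasting biomarker effects: "There were significant improvements in the Visual analogue scale score Osteoarthritis Research Society International responder index, HRQoL, and function at 26-week follow-up". Those are clinical outcomes, and the protocol goes on to say that the trial did not examine synovial markers. Nor does the result say anything about corticosteroids. No section states that a corticosteroid or NSAID changes any of the ten markers.
- A reader might infer that NSAID users stop on the day of the first aspirate. That is one reading of inclusion 5. Table 1 does not show everything done before the index visit: the radiograph and laboratory values needed for eligibility are absent from it, and the Consent section refers to a screening process. What can be said is that the start is unspecified.
- A reader might borrow 6 months as the look-back window because exclusions 6, 10 and 18 use it. Those windows concern gout, infection and experimental devices, and the experimental-drug window in item 18 is one month. The documents do not establish a window.
- Inclusion 3 requires walking pain of 41 to 90 mm, which tends to screen out patients still benefiting from an earlier injection. This mitigates the problem in part. It selects on pain and does not show that the joint fluid is free of earlier treatment.
- The modelled bias for inflammatory markers runs against the hypothesis. That does not make it harmless, since it could hide a real fall, and the hyaluronate bias has the opposite sign.

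None of these points supplies the missing rule or the missing record.

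**Conclusion.** The concern holds as a gap in eligibility and data collection that can bias the primary biomarker change, and it should be fixed. The protocol's own design makes it relevant: it samples at 6 months after the first injection set, so it already allows that a course may still affect the fluid months later, yet it neither excludes nor records such a course before Visit 1.

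The firmest part is hyaluronate, where residual product would raise the baseline and give a spurious fall; its size cannot be derived from the documents. For inflammatory markers, the spurious rise of about 4% to 32% rests wholly on assumed prevalence, assumed suppression and full recovery. At the low end the effect is minor; at the high end it could decide the result for a marker. The text supports high confidence in the omission, but not a claim about how much bias there is or which way it runs overall. The lack of a control arm remains the larger weakness of the pilot; this is one baseline influence within it that is cheap to limit.

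**What to change.** Three changes:

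1. Add an exclusion for a recent intra-articular hyaluronate or corticosteroid injection in the target knee before Visit 1. The clinical team should set the window and reconcile it with the protocol's own search for an effect at 6 months.
2. Add a Visit 1 history field, shown in Table 1, for the agent and date of the last target-knee injection and for recent NSAID use. State in inclusion 5 when acetaminophen-only use is taken to begin.
3. Before the first assay, pre-specify a sensitivity analysis of the biomarker change that excludes, or adjusts for, patients with recent NSAID use, with the interval that counts as recent fixed in advance.

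The cost is one eligibility line, one history field and one extra analysis. Some candidates will be deferred or lost, so enrolling 25 takes somewhat longer, and the sensitivity analysis will be imprecise at that size. If the exclusion is declined, the second item still lets readers see how many patients are affected, and the sensitivity analysis could be extended to recently injected knees.

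### Secondary outcomes: the design cannot test improved time to TKA, the TKA item states no surgery date, knee or procedure, and the 12-item instrument has two names

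*Combined protocol and SAP*

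**What the plan says.** - **Hypothesis** (Background and Significance): "we also hypothesize that Euflexxa therapy will improve pain, clinical outcomes, and time to total knee arthroplasty".
- **Design** (Research Procedures, Injection): "Twenty five patients will be assigned to receive Euflexxa (n=10"). No control group, historical cohort or reference rate is described anywhere.
- **TKA collection** (Secondary outcome measurements): time to TKA is the outcome, "which will be collected by asking questions regarding whether or not the patient received a total knee arthroplasty". This section and the text above Table 1 both have the question asked at every visit. The Table 1 row is headed Knee Surgery? and is marked at visits 1 to 6, 9 and 10, but not at 7 and 8.
- **Knee at entry** (Exclusion criteria, items 3 and 4): the two knees are treated separately, with "any surgery to the target knee within the prior 12 months" in one item and "surgery to the contralateral knee or other weight-bearing" in the next. The TKA outcome makes no such distinction.
- **12-item instrument**: the secondary outcome list has "Veterans Rand-12 item form (VR-12"). The text above Table 1 has "Short Form-12 (SF-12"), and the Table 1 row also says SF-12.
- **Analysis** (Data Analysis): a two-sided 0.05 threshold, and general linear models to adjust for BMI, gender, age and ethnicity. No time origin, censoring rule or time-to-event method is given.

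**The concern.** A claim that treatment improved time to TKA needs something to compare with. Pain and function scores have an index-visit value, so each patient offers a before-and-after contrast. TKA does not: every patient starts free of the event, and the only possible change is to have it. Without a control group or a stated reference, no result from this study could show that the time was lengthened.

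A time-to-event outcome also needs an event date. Because one knee is treated, it needs a side as well. A yes/no answer at widely spaced visits supplies neither, and a row about knee surgery in general does not separate TKA from other operations. A contralateral TKA could then be counted against the treated knee.

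The two instrument names leave the reader unable to say which 12-item score is the secondary outcome.

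**Working it through.** The plan gives no event count, power or precision figure for TKA, so there is none to reproduce. The checks below use Table 1 and the stated sample of 25. Weeks and days are converted at 30.44 days per month: 4 weeks = 0.92, 2 weeks = 0.46, 3 days = 0.10.

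**1. Instrument.** VR-12 appears once, in the outcome list, and never in the schedule. SF-12 appears in the schedule text and Table 1, and never in the outcome list. These texts contradict each other.

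**2. Dating a late TKA from a yes/no answer.** Visit 9 is at 12 ± 2 months and visit 10 at 24 ± 2 months.
- Nominal gap: 24 − 12 = 12 months, which is 12/24 = 50% of follow-up.
- Shortest: 22 − 14 = 8 months. Longest: 26 − 10 = 16 months.

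**3. The preceding gap depends on which text is followed.** Table 1 has "Visit 6 (6- month±4 weeks"), with visit 8 two weeks later ± 3 days.

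| Reading | Nominal (months) | Shortest | Longest |
|---|---|---|---|
| Table 1 (visit 6 to 9) | 12 − 6 = 6 | 10 − 6.92 = 3.1 | 14 − 5.08 = 8.9 |
| Text, every visit (visit 8 to 9) | 12 − 6.46 = 5.5 | 10 − (6.92 + 0.46 + 0.10) = 2.5 | 14 − (5.08 + 0.46 − 0.10) = 8.6 |

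The Aspiration section gives visit 6 a window of ± 2 weeks instead. The first row would then run from 10 − 6.46 = 3.5 to 14 − 5.54 = 8.5. The difference between the readings is small, but the contradiction is real.

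**4. What 25 patients can say about TKA.** These are exact (Clopper-Pearson) 95% intervals for a proportion, assuming status is known for all 25.
- 0 events: upper limit 1 − 0.025^(1/25) = 0.137, so 0 to 13.7%.
- 1 event: 0.1 to 20.4%.

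**5. Would an external reference rescue the hypothesis?** The documents give no reference risk, so a range is assumed. In an exact lower-tail test at 0.025 with 25 patients, even 0 events is significant only if the assumed 2-year risk exceeds 13.7%. The power to detect a halved risk is:

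| Assumed 2-year reference risk | Events allowed for significance | Power if risk is halved |
|---|---|---|
| 5% | none possible | 0% |
| 10% | none possible | 0% |
| 15% | 0 | 0.925^25 = 14% |
| 20% | 0 | 0.90^25 = 7% |
| 30% | 2 or fewer | 25% |

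Power does not rise steadily because the event count moves in whole numbers. A reference is possible in principle, but it would be imprecise at this size.

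**The case against.** The strongest reply is on date and knee. The outcome is called time to TKA and is collected by questions in the plural, so a form may well ask when and which side. Adverse events are recorded at all ten visits, with surgeon reports, and an inpatient stay meets the serious event definition. A reader might therefore infer either that these details will be captured or that they will not. The documents support neither inference. They do not exclude the details, and they do not say that any form or adverse event record supplies them for this outcome. The 8-to-16-month figure is therefore conditional, and it describes the longest gap between questions, not a typical one.

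Other replies stand in part:
- VR-12 against SF-12 may be a labelling slip. A reader might infer that the wrong questionnaire will be given, but nothing in the documents shows this. The contradiction still needs correcting.
- The figure n=10 beside twenty-five patients might suggest a second group of 15. No such group is described, so the figure needs reconciling but does not supply a comparator.
- The missing survival method is not peculiar to TKA. Data Analysis names no main analysis for any outcome and uses general linear models only for confounder control.
- Pilot status excuses low power. It does not excuse a stated hypothesis with nothing to compare against.
- A reader might infer that the 1- and 2-year scores are biased by surgery. The documents give neither a TKA count nor a surgical gain, so no size can be put on this, and it is zero if no TKA occurs.

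**Conclusion.** The concern holds in three parts, with different certainty.

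1. The instrument names contradict each other. This is plain from the text.
2. Improved time to TKA cannot be tested. This rests on the single treated group described, the absence of any reference and the absence of a baseline value. At best the study gives a descriptive rate with wide limits.
3. The TKA item is under-specified. Its consequence (12 months of uncertainty for a late TKA, 8 to 16 with windows, and no side) follows only if nothing beyond the stated answer is collected.

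Scores taken after a target-knee TKA are a minor point of unknown size.

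A reader might infer that the primary biomarker outcome is untouched. That is so only if no target-knee TKA occurs before visit 6, the last aspiration. The documents give no likelihood for such an event, so neither harm to the primary outcome nor its safety can be asserted. The point should be settled in the plan, but it does not undermine the study as a pilot.

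**What to change.** - Use one name, that of the instrument actually administered, in the outcome list, the schedule text and Table 1.
- Drop improved time to TKA as a hypothesis. Report target-knee TKA descriptively: the number of events and a Kaplan-Meier TKA-free estimate from the index visit, censored at last contact, with the number at risk. Give an exact 95% interval for the proportion only at a time when status is known for all patients. With dates recorded and everyone attending visit 10 within its window, that is month 24 − 2 = 22 at the latest. A prespecified external reference is the alternative, with the imprecision shown above.
- Add surgery date, knee (target or contralateral) and procedure type to the knee-surgery item. If another record already holds them, name it as the source.
- Reconcile the text that asks the question at every visit with Table 1, which leaves visits 7 and 8 blank.
- Flag scores taken after a target-knee TKA. No replacement rule is proposed.

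**Cost:** protocol wording, three form fields on a question already asked, and a weaker, descriptive claim about TKA.
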